## 6.2. Secondary Endpoints

The secondary endpoints for the study are:

1. Angiographic procedural success, defined as final diameter stenosis  $\leq 50\%$  in at least one of the Lacrosse NSE ALPHA attempted lesions following completion of the interventional procedure, including adjunctive stenting per core laboratory assessment.
2. Major adverse cardiac events (MACE) through hospital discharge per CEC adjudication. MACE is defined as a composite of:
  - All-cause death
  - Myocardial infarction
  - Clinically indicated target lesion revascularization
3. Stent thrombosis within the target vessel(s) through hospital discharge using ARC-2 definitions for definite & probable, per CEC adjudication.
4. Clinically significant arrhythmia (defined as those requiring intervention) through hospital discharge, per CEC adjudication.
5. Occurrence of Lacrosse NSE balloon rupture, per device deficiency case report form.
6. Change in minimum lumen diameter (MLD), measured by quantitative coronary angiography, following use of Lacrosse NSE ALPHA, per core laboratory assessment.
7. Device procedural success defined as for the primary endpoint, calculated and presented per target lesion.

Secondary endpoints 1 through 5 are defined at a subject level and will be presented as the proportion of subjects experiencing the above events. In cases where multiple events per subject may be observed (e.g., adverse events), the primary analysis will be at the subject level but total event counts will also be reported. Secondary endpoints 6 and 7 are defined at the lesion level and statistical analyses of these endpoints will account for within-subject correlation as some subjects will have more than one target lesion, using generalized estimating equations with an exchangeable correlation structure.

## 7. General Statistical Considerations

The following general comments apply to all statistical analyses and data presentations.

### 7.1. Descriptive Statistics

Continuous data will be summarized using descriptive statistics: mean, standard deviation, median, and range or interquartile range. Categorical variables will be summarized using frequency counts and percentages. For endpoints analyzed at the subject level that can occur more than once in a single subject, such as adverse events, the percentage will be based on the number of subjects experiencing the event; both subject and event counts will be reported. For endpoints analyzed at the lesion level (secondary endpoints 6 and 7 as defined above), the lesion-level analysis will be considered primary.

### 7.2. Significance Level

Hypothesis testing of the primary endpoint (against a predefined performance goal as defined below) will be performed using one-sided hypothesis tests at an alpha level of 0.05. Other statistical analyses will be performed using two-sided hypothesis tests at an alpha level of 0.05.

### 7.3. Duration Variables

Study Day 0 is the day of study device deployment (index procedure). Study day is calculated relative to day 0 and will appear in the listings where applicable:

Study Day = (Date of Event – Date of Study Device Deployment)

Duration variables will be calculated using the general formula:

[(end date – start date)]

### 7.4. Missing Data

All available data in the full analysis set will be used to evaluate study outcomes. Methods for replacing missing data, such as last value carried forward or multiple imputation, will not be employed for primary analyses; however, a sensitivity analysis of the primary endpoint incorporating worst-case assumptions (e.g., missingness equals failure) will be performed.

### 7.5. Software

All statistical analyses will be performed using Statistical Analysis System (SAS) for Windows (version 9.4 or higher, SAS Institute Inc. Cary, NC) or R (version 3.2 or higher, R Foundation for Statistical Computing, Vienna, Austria) or other widely accepted statistical or graphical software.

## 8. General Statistical Summaries

### 8.1. Subject Disposition

Subject accountability and study discontinuation will be summarized. Subject accountability at each visit will be summarized as the number of subjects with complete visits, missed visits, or study discontinuations prior to the visit. All subjects who do not complete the study will be tabulated by reason for discontinuation.

## 8.2. Demographic and Baseline Characteristics

Demographic and baseline characteristics will be summarized. Demographic variables will include, but are not limited to, age, gender and ethnicity.

## 8.3. Medical History

Medical history will be summarized. Medical history variables will include, but are not limited to, those related to the study disease history and current status as well as relevant concomitant conditions.

## 8.4. Adverse Events

An overall summary of adverse events will be presented. The summary will include the number and percentage of subjects who report at least one adverse event and the total number of adverse events. Complete subject listings of all adverse events will be provided. Adverse events as adjudicated by the CEC will be considered primary for the purpose of categorization, tabulation and reporting.

Adverse events adjudicated by the CEC as *definitely* or *probably* will be considered related adverse events for data analytic purposes. Events adjudicated by the CEC as *possibly*, *unlikely* or *not related* will not be considered related adverse events for data analytic purposes.

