7.5 Treatment Procedure & Immediate Post-Procedure Assessment

The PCI procedure will be performed following these guidelines:

- A maximum of one non-target lesion, if identified, must be located in a different coronary artery from the target lesion and must be treated first and deemed a clinical angiographic success, as visually assessed by the physician. Study devices cannot be used on this non-target lesion.
- Target lesion will be treated using the Lacrosse NSE ALPHA following the device instructions for use.
- A target lesion composed of multiple focal lesions that can be covered with one stent will be considered as a single lesion.
- A separate Lacrosse NSE ALPHA study device must be used for treatment of each target lesion.

Additional procedures and interventions may be performed per standard of care at the discretion of the treating investigator (except those defined in the exclusion criteria).

Post-procedure angiographic imaging of the target lesion must be captured and performed per the instructions provided by the core laboratory and must be captured in the same precise manner as was used for the pre-procedure images. Angiographic images must be sent to the core lab following the instructions provided by the core laboratory.

Standard PCI procedural data will be collected on the eCRFs, such as:

- Vessel and lesion characteristics, including MLD and diameter stenosis (%)
- TIMI grade flow pre- and post-treatment
- Type and size of study devices used, including lot number
- Device performance assessment, including balloon slippage
- Procedural durations, including start/end times
- Air kerma (Gy) and total fluoroscopy time

- Adverse event assessment, including perforation and dissection classifications
- Device deficiency assessment

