11.4 Adverse Event Relatedness

The investigator and the CEC will assess the relatedness of adverse events to the investigational device and the study procedure using the categories listed below (see **Section 13.1** for definitions):

- Definitely
- Probably
- Possibly
- Unlikely
- Not Related

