13.0 DEFINITIONS

13.1 Adverse Event Definitions

Adverse event: Untoward medical occurrence, unintended disease or injury, or untoward clinical signs (including abnormal laboratory findings) in subjects, users, or other persons, whether or not related to the investigational medical device and whether anticipated or unanticipated.

Adverse event relatedness: The relationship of an adverse event to the investigational device or the study procedure based on the categories defined below.

Relatedness	Description
Definitely	The adverse event follows a strong temporal sequence to the receipt (or attempted receipt) of the device treatment or procedure. This can include an adverse event that occurs after the study procedure.
Probably	The adverse event follows a reasonable temporal sequence to the receipt (or attempted receipt) of the device treatment or procedure, and the possibilities of other factors, such as underlying and concomitant illness, concomitant medications, or concurrent treatment can be excluded.
Possibly	The adverse event follows a reasonable temporal sequence from receipt (or attempted receipt) of the device treatment or procedure and the possibility of device treatment or procedure involvement cannot be excluded. However, other factors such as underlying or concomitant illness, concomitant medications, or concurrent treatment are presumable.
Unlikely	The adverse event has an improbable temporal sequence to the receipt (or attempted receipt) of the device treatment or procedure, or it can be reasonably explained by other factors, including underlying or concomitant illness, concomitant medications, or concurrent treatment.
Not related	The adverse event has no temporal sequence to the interventional procedure, the device treatment, or any user handling, or it can be explained by other factors, including underlying disease or concomitant illness, concomitant medication, or concurrent treatment.

Device deficiency: Inadequacy of a medical device with respect to its identity, quality, durability, reliability, usability, safety, or performance. [ISO 14155 2020, 3.19]

- Note: Device deficiencies include malfunctions, use errors, and inadequacy in the information supplied by the manufacturer including labelling. This definition includes device deficiencies related to the investigational medical device.

Serious adverse event (SAE): An adverse event that led to any of the following:

- Death

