- Type D: Spiral ("barber shop pole") luminal filling defects, frequently with excessive contrast staining of the dissected false lumen
- Type E: Appear as new, persistent filling defects within the coronary lumen
- Type F: Dissections that lead to total occlusion of the coronary lumen without distal antegrade flow

Note: Type E and F dissections may represent thrombus

Major adverse cardiac events (MACE): A composite of all-cause death, MI, and clinically indicated TLR. Classification of an event as a MACE will be performed by the CEC.

Minimum lumen diameter (MLD): The mean minimum lumen diameter (typically measured in-lesion, in-stent, and in-segment) derived from two orthogonal views by QCA (Jonas).

Myocardial infarction (MI): The ARC-2 definition of myocardial infarction (Garcia-Garcia) is as follows:

- Absolute rise in cardiac troponin (from baseline) $\geq 35 \times$ upper reference limits *and*
- One or more of the following criteria
 - New significant Q waves or equivalent. Significant is defined as the development of new Q waves ≥ 40 ms in duration and ≥ 1 mm deep in voltage in ≥ 2 contiguous leads.
 - Flow-limiting angiographic complications
 - New "substantial" loss of myocardium on imaging

Perforation classifications (Ellis):

- Type I: Extraluminal crater without extravasation.
- Type II: Pericardial or myocardial blush without contrast jet extravasation.
- Type III: Extravasation through frank (≥ 1 mm) perforation.

Procedural success: Successful delivery, inflation, deflation, and withdrawal of the study balloon without evidence of vessel perforation, flow limiting dissection (grade C or higher) or

reduction in TIMI flow from baseline that was related to the study device (per CEC adjudication) and final TIMI flow grade of 3 at the conclusion of the PCI procedure.

Reference vessel diameter (RVD): The average of normal segments within 10 mm proximal and 10 mm distal to the target lesion from two orthogonal views using QCA

Stent thrombosis: According to ARC-2 (Garcia-Garcia), definite stent/scaffold thrombosis is considered to have occurred by either angiographic or pathological confirmation and is defined as:

Definite stent thrombosis

Angiographic confirmation of stent/scaffold thrombosis:

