## 6.1. Primary Endpoint

The primary endpoint is defined as device procedural success, defined as:

- Successful delivery, inflation, deflation, and withdrawal of the study balloon; and
- No evidence of device-related vessel perforation, flow limiting dissection (grade C or higher per Clinical Events Committee (CEC) adjudication) or reduction in thrombolysis in myocardial infarction (TIMI) flow from baseline (per core laboratory assessment); and
- Final TIMI flow grade of 3 at the conclusion of the PCI procedure per core laboratory assessment.

This endpoint will be presented as the proportion of subjects experiencing device procedural success. The proportion of target lesions meeting the primary endpoint will be concurrently calculated and presented as a secondary endpoint, as noted below.

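### Do overlapping causality categories leave the score for device-related complications in the primary endpoint undetermined?

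*SAP*

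**What the plan says.** SAP 6.1 makes this a component of device procedural success: "No evidence of device-related vessel perforation, flow limiting dissection (grade C or higher per Clinical Events Committee (CEC) adjudication"). It adds no reduction in TIMI flow from baseline and a final TIMI grade of 3, both read by the core laboratory. Protocol 13.2 attaches the causal qualifier to the complications as a group, ending with "reduction in TIMI flow from baseline that was related to the study device (per CEC adjudication").

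Protocol 11.4 has the investigator and the CEC "assess the relatedness of adverse events to the investigational device and the study procedure using the categories listed below": definitely, probably, possibly, unlikely, not related. Protocol 13.1 describes each one. For *definitely*: "The adverse event follows a strong temporal sequence to the receipt (or attempted receipt) of the device treatment or procedure". *Unlikely* has an alternative limb, "or it can be reasonably explained by other factors, including underlying or concomitant illness, concomitant medications, or concurrent treatment", and so does *not related*: "or it can be explained by other factors, including underlying disease or concomitant illness, concomitant medication, or concurrent treatment".

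SAP 8.4 makes the CEC's adjudication primary and counts definitely and probably as related. It then states: "Events adjudicated by the CEC as *possibly*, *unlikely* or *not related* will not be considered related adverse events for data analytic purposes". Neither SAP 6.1 nor SAP 9.1 says in words that this cut decides device-relatedness for the primary endpoint.

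Protocol 9.1 sets up a CEC of at least three non-investigator interventional cardiologists, who adjudicate both adverse events and endpoints under written guidelines. Those guidelines are not among the documents reviewed.

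**The concern.** Taken literally, the five descriptions are not mutually exclusive. *Definitely* needs timing alone; only *probably* requires other causes to be ruled out. The second limbs of *unlikely* and *not related* are joined by an 'or', so they apply whatever the timing once another explanation is available. No precedence rule is given, and the two ends of the scale fall on opposite sides of the SAP 8.4 cut.

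Protocol 7.5 makes the situation realistic: "Additional procedures and interventions may be performed per standard of care at the discretion of the treating investigator". Suppose a grade C dissection is first seen after the study balloon and then a stent have been used in the lesion. Its timing is close, and another treatment could explain it. If it is rated at the top of the scale, the subject is a failure. If it is rated at the bottom, the subject is a success, provided the other components are met.

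The table also speaks of the device treatment or the procedure together, whereas the endpoint concerns the device alone. In an open-label single-arm trial tested against a fixed goal, a few subjects scored the other way could decide the result. The only sensitivity analysis planned for the primary endpoint addresses missing data, not classification.

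**Working it through.** **1. The plan's own figure.** Inputs: n = 200, performance goal p0 = 0.877, assumed rate p1 = 0.935, exact one-sided binomial test at 0.05 (SAP 9.1 and 10). The pass line is the smallest r with P(X ≥ r | 200, 0.877) ≤ 0.05.

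- P(X ≥ 183) = 0.0580, which fails.
- P(X ≥ 184) = 0.0351, which passes, so r = 184 (at most 16 failures).
- Power = P(X ≥ 184 | 200, 0.935) = 0.843, against 84% stated.
- With 5% missing, n = 190 and r = 175; power is 0.825, against above 80% stated.

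The design arithmetic is sound and does not depend on how causality is worded.

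**2. The rows side by side.**

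| Category (Protocol 13.1) | Timing | Other causes | Side of SAP 8.4 cut |
|---|---|---|---|
| Definitely | strong | not mentioned | related |
| Probably | reasonable | excluded | related |
| Possibly | reasonable; involvement not excluded | presumable, concurrent treatment included | not related |
| Unlikely | improbable, **or** → | reasonable alternative explanation | not related |
| Not related | none, **or** → | alternative explanation | not related |

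The literal overlap between the first row and the last two is there.

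**3. The example tested against every row.** For a dissection first seen after balloon and stent, timing is reasonable, the balloon cannot be excluded, and the stent is a presumable cause. That is the *possibly* row almost point for point, and SAP 8.4 says how *possibly* is counted. To reach *definitely*, a rater must ignore the meaning of the label and call the sequence to the balloon strong although the stent came later. To reach *not related*, a rater must set aside the balloon's involvement altogether. Used as a graded scale, the table gives one answer.

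**4. Device or procedure.** Protocol 11.1 and 11.4 have relatedness assessed to the device and to the procedure. The lead-in to the 13.1 table names the device or the procedure, so the combined phrase in the rows can be read as shared wording for whichever is being rated. The endpoint says device-related, and Protocol 13.2 ties it to the study device by CEC adjudication. The rating required is therefore identifiable.

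**5. How much could move.** Let k be the number of subjects whose score depends on the disputed reading, all moving the same way, with X ~ Bin(200, 0.935).

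- If 93.5% is the lenient rate, the verdict differs when 184 ≤ X ≤ 183 + k.
- If 93.5% is the stricter rate, it differs when 184 − k ≤ X ≤ 183.

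| k | 93.5% lenient | 93.5% stricter |
|---|---|---|
| 1 | 7.3% | 5.5% |
| 2 | 16.4% | 9.4% |
| 4 | 38.3% | 13.6% |

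At the planned result, 187/200 (p = 0.0053), four adverse changes give 187 − 4 = 183 and a fail.

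These figures describe how steep the pass line is; they do not measure the wording. To count towards k, a subject must have a qualifying complication, no device-use failure, a final TIMI grade of 3, and a genuinely disputed cause. The documents give no frequency for that combination. The nearest figures, 13/200 failures in the Scoreflex NC trial and 4/188 in the pooled LOX studies, count failures of every kind. k = 4 would equal 4/13 = 31% of all the Scoreflex NC failures, and the 38.3% figure adds those four to an expected 200 × 0.065 = 13 failures.

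**The case for a change.** The strongest case for a change is that a pre-specified endpoint should be readable from the protocol and SAP alone. The CEC will settle on one category, but the wording would support more than one, and the guidelines that might break the tie cannot be seen. SAP 8.4 is an adverse-event section, so its use for the primary endpoint is an inference; if it does not apply, device-related has no written analytic rule. Requiring a final TIMI grade of 3 does not remove the problem, since a treated dissection can still end with normal flow.

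The description of the text stands. *Definitely* is looser than *probably* on other causes, the 'or' limbs are too wide, and the link from SAP 8.4 to SAP 6.1 is unwritten.

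The claim that the score is left open does not follow. Analysts would apply the only stated cut to the CEC's device rating, and a sentence to that effect would merely record it. A direct yes-or-no endpoint adjudication by the CEC, which Protocol 9.1 also allows, would likewise give one answer per event. Rewriting the five categories with new likelihood thresholds and a tie-break would replace one judgement scale with another. It would also require events already adjudicated to be rated again, with no demonstrated gain in accuracy. Causal attribution after several devices in one lesion remains expert judgement under any wording.

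**Conclusion.** No change to the plan is needed. The category descriptions are loosely drafted and overlap if each row is read in isolation. The plan nevertheless supplies what scoring needs: a committee of at least three non-investigator interventional cardiologists, written guidelines, a five-level scale, a stated cut, and an endpoint that names the device. The case that prompts the worry fits the middle category, and the SAP says how that is counted.

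The result is sensitive near the pass line, since one subject separates 184/200 (p = 0.035) from 183/200 (p = 0.058). That holds for any source of classification error in this design. The number of subjects affected by this particular wording is an assumption, the direction is unknown, and no bias is shown.

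This conclusion assumes that the CEC records one device rating per event and that its guidelines do not contradict SAP 8.4. The documents neither state nor contradict either assumption.

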# 9. Analysis of Study Endpoints

## 9.1. Primary Endpoint

The primary endpoint will be presented as the proportion of subjects experiencing device procedural success.

These results will then be compared to a performance goal derived from studies of comparable products. As clinical evidence from FDA premarket approval (PMA) application submissions on similar products (e.g., AngioSculpt, Fx miniRAIL) involve a substantially different definition of the primary endpoint, the performance goal is based on recent studies in the LOX product code, as follows:

Device	N	Endpoint	Success Rate
Sapphire II PRO	61	Successful use, no perf or grade C dissection, no reduction in TIMI, final TIMI 3	96.7% (59/61)
Emerge	60	Successful use, no perf or grade C dissection, no reduction in TIMI, final TIMI 3	98.3% (59/60)
Mini Trek Rx	71	Successful use, no clinically significant perf or grade C dissection, no clinically significant arrhythmias, no reduction in TIMI, final TIMI 3	98.5% (66/67  )
TOTAL			97.9% (184/188)
1 Angiographic documentation associated with predilation with the study device was not available for 4 patients; accordingly, patient-level analysis related to the primary endpoint was performed for 67 patients.			

The sample-size weighted rate of endpoint success in the above trials is then 97.9% as shown above.

Results are also available from the Scoreflex NC trial (Kandzari et al.), which included a comparable primary endpoint which was achieved in 93.5% (187/200) of study subjects; as the product and intended patient population in the Scoreflex NC trial are substantially more similar to those in the present study than in the LOX studies cited above, it is prudent to account for these results.

To do so without overreliance on Scoreflex NC alone, we therefore adjust the tabulated outcomes from the LOX studies above by half of the difference compared to Scoreflex NC, or  $(97.9\% - 93.5\%) / 2 = 2.2\%$ , to get a final value of 95.7%.

The studies cited above did not have statistical performance goals defined, while other trials with similar purposes and populations (e.g., AngioSculpt) used different endpoints; however, in general in the PCI space statistical margins such as 7% (e.g., FX miniRAIL), 9.4% (e.g., Asahi Intecc) and 10% (e.g., XIENCE) have been applied. Therefore, a value of 8%, within the typical range, will be applied.

With this statistical margin (i.e., delta), the performance goal is then 87.7%. Formally, the hypotheses to be tested for the primary endpoint are then as follows:

$$H_0: r \leq PG$$

$$H_A: r > PG,$$

where  $r$  is the proportion of endpoint successes and  $PG$  is the performance goal of 87.7% = 0.877.

The hypotheses will be tested at a one-sided alpha level of 0.05 and endpoint success will be declared if the performance goal is met (i.e., if the null hypothesis above is rejected in favor of the alternative hypothesis). For primary analysis, this endpoint will be tested on all subjects with available data, with a worst-case sensitivity analysis also incorporated as noted below.

Among the 200 subjects intended for enrollment, a subgroup of at least 30 is intended to be cases of in-stent restenosis. The value of 30 is a commonly used benchmark and is chosen to provide a reasonable sample size to characterize outcomes in this subgroup, as well as a feasible target from a clinical perspective. The ISR subgroup is not intended for formal statistical hypothesis testing independent of the entire study cohort as the study is powered for the full 200 subjects planned for enrollment; hence no decision rule specific to ISR cases is defined. However, key outcomes, including the primary endpoint, will be compared between the *de novo* and ISR cohorts to assess any statistically significant differences. This testing will be performed on an exploratory basis and hence no alpha allocation for multiplicity is necessary, nor will overall analytical conclusions be driven by the number of ISR cases.

To obtain at least 30 ISR subjects, enrollment will continue until both the overall target of 200 and the ISR cohort of 30 have been obtained. More specifically, enrollment of non-ISR subjects will be capped at 170 such that if and when this maximum has been achieved without 30 ISR subjects,

only ISR subjects will be permitted to be enrolled until the minimum of 30 has been reached, for a total of 200 subjects.

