7.6 Early Withdrawal / Premature Discontinuation of Subjects

Subjects may be withdrawn early from the study for several reasons including:

- Subject death
- Subject request for withdrawal (withdrawal of consent)
- Investigator decision, to be fully documented
- Adverse event

If a subject is discontinued from the study early, a Study Completion eCRF must be completed describing the reason for early discontinuation. If a subject chooses to withdraw from the study and also withdraws consent for disclosure of further information, no further evaluation(s) should be performed, and no additional data collected. The sponsor may retain and continue to use any data collected prior to the withdrawal of consent.

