## **10. Determination of Sample Size**

Based on the performance goal and hypothesis testing specified above, sample size and power were computed using SAS version 9.4 PROC POWER, assuming an exact test of a single binomial outcome against a performance goal (the null hypothesis). Postulating a primary endpoint success rate at the subject level of 93.5%, as observed in the Scoreflex NC trial, and with a null hypothesis of 87.7% per the performance goal constructed from the available literature, a sample size of 200 subjects provides 84% power to meet the endpoint using hypothesis testing as defined above. Under modest assumptions for missing data on study outcomes (e.g., 5% missingness), the power remains above 80%.

This sample size also reflects clinical trial practice in the space and in the study population of interest and matches the sample sizes from relevant regulatory studies including the Scoreflex NC and AngioSculpt primary clinical investigations.

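### An enrolled subject whose procedure ends by death, surgery or abandonment before a gradable closing angiogram can drop out of the primary test instead of counting as a failure

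*SAP*

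**What the plan says.** The primary endpoint (SAP 6.1, Protocol 5.1) is met only if three components all hold: (1) the study balloon is delivered, inflated, deflated and withdrawn successfully; (2) there is no device-related perforation, flow-limiting dissection or fall in TIMI flow; and (3) "Final TIMI flow grade of 3 at the conclusion of the PCI procedure per core laboratory assessment".

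Protocol 7.2.2 counts a patient as enrolled when the study catheter enters the guiding catheter, before any post-treatment image exists. SAP 5 and Protocol 8.1 base the primary analysis on whatever data are available for enrolled subjects.

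On the test itself, SAP 9.1 and Protocol 8.3 say: "For primary analysis, this endpoint will be tested on all subjects with available data". The same sentence adds that a worst-case sensitivity analysis will be done. On missing values, SAP 7.4 and Protocol 8.8 say: "Methods for replacing missing data, such as last value carried forward or multiple imputation, will not be employed for primary analyses". They then describe the sensitivity analysis, with missing counted as failure given as an example. Endpoint success is declared from the primary test against the performance goal; the sensitivity analysis has no stated part in that decision.

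Neither document says that one known component failure settles the endpoint. Neither says how to score a subject with no final TIMI grade because the procedure ended early.

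**The concern.** A lost or unreadable angiogram from a completed procedure is missing data. A procedure that ends by death, emergency surgery or abandonment before final flow can be shown is an outcome, and a bad one. The available-data rule does not separate the two.

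The exposed group is narrow. Components 1 and 2 must not already have failed the subject: the balloon went in, worked and came out, no device-related component-2 event was adjudicated, and the procedure then ended without a gradable closing image. Component 3 cannot then be assessed and nothing is imputed, so a literal reading leaves the subject out of the test. Leaving out subjects of this type can only raise the observed success rate. The classification would also be settled after the event, when one subject may decide whether the performance goal is met.

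**Working it through.** **Inputs.** Planned N = 200 (Protocol 6.2, SAP 10). Null rate 0.877: SAP 9.1 "is the performance goal of 87.7% = 0.877". Level: "The hypotheses will be tested at a one-sided alpha level of 0.05". Design alternative 0.935: SAP 10 "Postulating a primary endpoint success rate at the subject level of 93.5%, as observed in the Scoreflex NC trial". Exact binomial test (SAP 10). The share of subjects dropped is not in the documents and is varied below.

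**1. The plan's own figure.** The pass mark c(n) is the smallest r with P(X ≥ r | n, 0.877) ≤ 0.05.
- n = 200: c = 184, attained level 0.0351, power at 0.935 = 0.843. The stated 84% reproduces.
- n = 190 (5% missing): c = 175, power 0.825. The statement that power stays above 80% reproduces.

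So with all 200 subjects scored, at most 200 − 184 = 16 failures are allowed.

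**2. Effect of dropping m failed subjects.** The numerator stays the same and the denominator falls to 200 − m.

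| m dropped | Available-data test | Same successes over 200 |
|---|---|---|
| 1 | 183/199, p = 0.037, pass | 183/200, p = 0.058, fail |
| 2 | 182/198, p = 0.039, pass | 182/200, p = 0.091, fail |
| 3 | 181/197, p = 0.041, pass | 181/200, p = 0.135, fail |
| 6 | 178/194, p = 0.048, pass | 178/200, p = 0.334, fail |

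For m from 0 to 6 the test still tolerates 16 observed failures, so up to 16 + 6 = 22 true failures in 200 could be declared a success. At m = 7 the tolerance falls to 15 observed failures (pass mark 178/193).

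**3. False-pass rate.** Let the true success rate over all enrolled subjects be 0.877 and let a share s of subjects be failures that leave the denominator. Then m ~ Bin(200, s), and given m the successes are Bin(200 − m, 0.877/(1 − s)). The false-pass rate is the sum over m of P(m) × P(successes ≥ c(200 − m)).

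| Assumed s | Expected number in 200 | s as share of all failures (s/0.123) | False-pass rate |
|---|---|---|---|
| 0 | 0 | 0 | 3.5% |
| 0.25% | 0.5 | 2% | 4.4% |
| 0.5% | 1 | 4% | 5.4% |
| 1% | 2 | 8% | 8.2% |
| 2% | 4 | 16% | 16.4% |

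Because the attained level with no dropping is 3.5%, there is some slack. The nominal 5% is passed at about one expected subject in 200.

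**4. Why not count all missing as failure in the primary test?** Suppose images are lost at random, the true rate is 93.5%, and every loss is scored a failure. The success probability becomes 0.935 × (1 − share lost), with pass mark 184/200. Power is then 68% at 1% lost, 40% at 2.5% and 9% at 5%. The rule therefore has to turn on why the grade is missing.

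**The case against.** **Most bad procedures already fail.** The endpoint is a conjunction, so a careful analyst would fail a subject whose study balloon could not cross (component 1) or who had a device-related perforation or grade C or higher dissection (component 2), with or without a final TIMI grade. A reader might infer that the plan removes all of the worst cases; it does not. This stands, and it confines the point to the narrow group described above. Even the conjunction logic is left unwritten, though.

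**The discrepancy would be visible.** The planned worst-case analysis would show 183/200 beside 183/199. That also stands, but it does not decide success. Because it fails lost images too, an unfavourable result could be explained away as technical loss.

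**The events may be rare.** Entry criteria exclude shock or unstable hemodynamics, recent type I infarction, low ejection fraction, target-lesion thrombus, chronic occlusion and unprotected left main disease. No document supports a share as high as 2%, and the flip examples sit at the pass boundary by construction. Images lost from successful cases also leave the denominator, so not all removal favours the device.

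**Two passages invite too strong a reading.** In the performance-goal table, the footnote to one source trial says "patient-level analysis related to the primary endpoint was performed for 67 patients", out of 71. A reader might take this as a precedent for dropping catastrophes. It describes unavailable angiographic documentation and mentions no death, surgery or abandonment. Protocol 7.6 ("Subjects may be withdrawn early from the study for several reasons including") lists death and adverse events, but it concerns leaving the study and does not say such subjects are removed from the analysis.

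**Conclusion.** The point holds as a gap in how the deciding analysis is specified. Under the plan's wording, a subject whose procedure ended before a gradable closing image, with components 1 and 2 not failed, can be excluded; the documents do not say that such a subject will be. One exclusion is enough to turn 183 successes from a fail into a pass.

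A reader might go further and conclude that the one-sided 5% error rate is not kept. The documents do not support that unconditionally. It depends on how many such subjects occur and on how they are handled. At an assumed 0.25% the false-pass rate is about 4.4%, still under 5%; at 0.5% it is about 5.4%, and it rises from there. The calculation assumes that every subject in the assumed share is a true failure and is dropped, and that no other data are missing.

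The change is worth making before outcome data are reviewed, because the rule is cheap and the bias from this group runs only in the device's favour.

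**What to change.** In SAP 7.4 and 9.1, and in Protocol 8.3 and 8.8, state that in the primary analysis:

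- (a) a subject with any component known to have failed is a failure, whatever else is missing;
- (b) a subject whose final TIMI grade is missing because the index procedure ended by death, conversion to surgery or abandonment is a failure;
- (c) only subjects with a completed procedure whose images are lost or unreadable are treated as missing.

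Keep the worst-case sensitivity analysis for group (c).

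**Cost.** A few sentences and no extra subjects. The existing allowance for 5% technically missing images is unaffected (power 82.5% at n = 190). The reported success rate may be slightly lower. The reason for a missing final image must be recorded. The Study Completion eCRF asks why a subject left the study early, but a subject sent to surgery need not leave it, and the procedural items listed in Protocol 7.5 do not name abandonment or conversion. A field may have to be added if the forms do not already capture this.
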